We will compare expression levels of the organ-specific proteins in the two groups of patients, using a cross-sectional design. Longitudinal progression within individual patients will be left for Specific Aim 2. Given the complications of sampling error for each phenotype, the preferred design is cross-sectional, informed by knowledge that the patients with fibrosis did not progress to cirrhosis on follow-up biopsies, allowing clear separation of the groups.

Sample Size. For this pilot study, we plan the sample size to detect a relative difference of 40% in protein levels between any two groups of patients in the pairwise comparisons between fibrosis and cirrhosis. Assuming a coefficient of variation of <0.5 , we would have at least 80% power to detect the difference with 20 patients per group.

Statistical Analysis Plan. Multiple linear regression will be used to assess the effects of candidate liver-specific proteins associated with the list of MRM peptides. Transformations will be considered should model diagnostics plots reveal any evidence of departure from linearity. In a secondary analysis, we will reverse the problem formulation with the disease category (fibrosis, cirrhosis, HCC) being the response while protein expression levels are the explanatory variables. Due to small sample size, principal component analysis on protein expression will be used to reduce the dimension of the feature vector with the first two/three principal components entering a multinomial logistic regression model. Since data are sampled based on the disease status, no prediction of absolute probabilities of the type of disease based on the protein level will be attempted. The focus will be on identifying significant relative effects potentially allowing us to discriminate between the pairs of disease categories.

4.2 Specific Aim 2, Validation Study: Validate serum biomarker findings from Aim 1 in a larger number of HALT-C specimens (independent of those used in Aim 1) to evaluate usefulness of this panel in the diagnosis of hepatitis C-related cirrhosis and in the prediction of progression of liver disease.

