We will proceed with aim 2 only if results of aim 1 are positive. Based on the results of Aim 1, a panel of serum biomarkers that differentiates patients with Ishak 3 or 4 and no histological or clinical outcome and patients with Ishak 5 or 6 who developed clinical outcome will be assembled. Results will be considered positive if this panel offers an accuracy $\geq 70\%$ in differentiating these two groups of patients.

We request serum specimens from a total of approximately 150 patients: 30-40 patients with baseline biopsy showing Ishak 3 or 4 and no progression to histological cirrhosis, clinical decompensation, or HCC; 30-40 patients with baseline biopsy showing Ishak 3 or 4 and progression to histologic cirrhosis but no clinical decompensation or HCC; 30-40 patients with baseline biopsy showing Ishak 5 or 6 and no

progression to clinical decompensation or HCC, and 30-40 with baseline Ishak 5 or 6 and progression to clinical decompensation but not HCC. For those who progressed, we would like to obtain 2 earlier samples at baseline and approximate midpoint to time of cirrhosis or clinical decompensation. It would be desirable to match groups for gender, ethnicity, and HCV genotype.

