Statistical Analysis Plan: As for Aim 1, we will use multiple linear regression with the disease status as a categorical covariate. Adjusted R-Squared, Mallow's Cp, and AIC criteria will be used to ensure reproducibility of the predictive properties of the protein panel in future observations. In order to handle multiple observations made on a subset of study subjects, a random intercept term will be introduced in the linear mixed model. As a secondary analysis, survival analysis methods (proportional and non-proportional hazards regression models) will be used on a subset of subjects with follow-up information on their progression from fibrosis to cirrhosis and/or HCC during the follow-up. There is insufficient information at this point to assess the power and precision of the validation analysis. Therefore, updated sample size assessment will be performed after Aim 1 has been completed, yielding quantitative data on coefficient of variation and on group differences by protein. Tentatively, using the same assumptions as in Aim 1, we expect to have improved sensitivity with 30 patients per group, instead of 20, resulting in an ability to detect a 27% difference in protein levels. We will analyze both individual proteins and all proteins, as well as potentially related, clustered proteins as secondary analyses.

5. Methods & Data Usage

a) Novel technology platforms: Next generation deep sequencing for transcripts (such as Solexa); N-glycopeptide proteomics and multiple reaction monitoring for proteins by mass spectrometry.

b) Protein biomarker panel: See Table 1 for proteins and MRM peptides to be assayed.

c) Assays of liver and serum specimens: We will use multiple reaction monitoring of the 2 or 3 specific peptides associated with each of the 36 proteins in the Table below in an Orbitrap or LTQ-FT mass spectrometer; the peptides have already been designed (Table 1).

d) Statistical design and analysis: See specific sections under Aim 1 and Aim 2.

e) Data usage: We will fully comply with the HALT-C Data Use Agreement. Samples will be labeled with HALT-C subject no. and sample ID. We have no interest in specific-patient identifiers. We will use newly-generated identifiers held by the HALT-C PI to permit longitudinal analyses of serum specimens from the patients studied. We will report all findings on a group basis.

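### Aim 2's primary analysis compares protein levels between disease groups, so it does not re-test how well the Aim 1 panel classifies patients, which is the aim's stated purpose

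*Protocol*

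**What the plan says.** - **Purpose (section 4.2).** Findings from Aim 1 are to be validated in independent specimens "to evaluate usefulness of this panel in the diagnosis of hepatitis C-related cirrhosis and in the prediction of progression of liver disease". Section 6(c) repeats that Aim 2 tests differentiation and prediction.
- **Primary model (section 4.2, Statistical Analysis Plan).** "As for Aim 1, we will use multiple linear regression with the disease status as a categorical covariate". A random intercept handles repeat samples.
- **Direction of the model (section 4.1, Statistical Analysis Plan).** The model with disease as outcome is a secondary analysis and is described as a reversal: "we will reverse the problem formulation with the disease category (fibrosis, cirrhosis, HCC) being the response while protein expression levels are the explanatory variables".
- **Evidence of reproducibility (section 4.2).** Adjusted R-squared, Mallows' Cp and AIC are named, and the sentence ends: "AIC criteria will be used to ensure reproducibility of the predictive properties of the protein panel in future observations".
- **Prediction (section 4.2).** Proportional and non-proportional hazards models are secondary. They use a subset with follow-up on progression from fibrosis to cirrhosis and/or HCC.
- **Accuracy (section 4.2 and Part III).** "Results will be considered positive if this panel offers an accuracy" of at least 70%. This is the condition for starting Aim 2.
- **Status of these texts.** Sections 5(d) and 7 refer the reader to the Aim 1 and Aim 2 sections for the statistical analysis plans.

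**The concern.** A validation study of a diagnostic panel has to show how well a fixed rule sorts new patients. The primary model written for Aim 2 answers another question: how far average protein levels differ between disease groups. A clear difference in means can go with poor separation of individuals.

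The only performance threshold in the protocol is the 70% gate. It is met or missed in Aim 1, in a comparison of non-progressing Ishak 3-4 patients with cirrhotic patients who later decompensated. Aim 2 adds the two intermediate groups (fibrosis that progresses to cirrhosis, and cirrhosis that stays compensated), where separation may well be harder. If Aim 2 is run as written, its primary result will not say whether the panel's accuracy holds there.

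**Working it through.** **1. Which way the model runs.** Section 4.1 opens by speaking of the effects of candidate proteins, which alone could be read either way. Section 4.2 makes disease status a covariate, and section 4.1 calls disease-as-response the reverse formulation. Taken together, protein level is the response in the primary model, and its coefficients are differences in mean protein level between groups.

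**2. What the three criteria measure here.** Adjusted R-squared, Cp and AIC are computed from the residuals of the fitted model with a penalty for its size. With protein level as response, they say how well disease status and other covariates account for that protein. They do not score the classification of a patient.

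**3. The plan's own Aim 2 figure.** Section 4.2 gives a detectable difference of 27% with 30 per group on Aim 1 assumptions (40% with 20 per group, CV below 0.5). It does not reproduce: scaling by the square root of n gives 40% × √(20/30) = 33%, while 40% × 20/30 = 26.7%. That is a separate matter, and nothing here depends on it.

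**4. Mean difference against classification.** Assume one normally distributed marker with equal variances, and CV 0.5 as the limiting case. Then d = difference/CV, AUC = Φ(d/√2), and best accuracy with equal groups = Φ(d/2).

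| Difference | d | AUC | Best accuracy |
|---|---|---|---|
| 27% | 0.27/0.5 = 0.54 | Φ(0.382) = 0.65 | Φ(0.27) = 61% |
| 40% | 0.40/0.5 = 0.80 | Φ(0.566) = 0.71 | Φ(0.40) = 66% |

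Accuracy of 70% needs d = 2 × 0.5244 = 1.05, a difference of 0.5 × 1.05 = 52%. The result depends on the CV. At CV 0.3, a 27% difference gives Φ(0.45) = 67% and a 40% difference gives Φ(0.667) = 75%. A panel may also do better than one protein. So a detected mean difference does not settle whether 70% is reached.

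**5. Precision of the 70% gate.** An observed 28/40 (70%) in Aim 1 has an exact 95% interval of 53.5% to 83.4%, before any allowance for building the panel on the same patients.

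**6. What the Aim 2 samples could deliver.** Groups are 30-40 each. Pooling two per stage gives 60-80 versus 60-80 for Ishak 5-6 versus 3-4. A within-stage contrast is 30-40 versus 30-40. Hanley-McNeil variance with n per side:

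Var = [A(1−A) + (n−1)(u−A²) + (n−1)(v−A²)]/n², where u = A/(2−A) and v = 2A²/(1+A).

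The AUC is an assumption, since no document gives one. At A = 0.75: u = 0.600, v = 0.643, A² = 0.5625.

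- n = 70: (0.1875 + 69×0.0375 + 69×0.0804)/4900 = 0.00170; SE 0.0412; half-width 1.96 × 0.0412 = 0.081. At n = 60 and 80: 0.087 and 0.076.
- n = 35: (0.1875 + 34×0.0375 + 34×0.0804)/1225 = 0.00342; SE 0.0585; half-width 0.115. At n = 30 and 40: 0.124 and 0.107.
- For AUC from 0.65 to 0.85, the half-width runs from 0.091 to 0.065 at n = 70 and from 0.129 to 0.092 at n = 35.

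Sensitivity of 70% in 70 patients: 1.96 × √(0.7 × 0.3/70) = 0.107. Overall accuracy of 105/150 (70%): exact 95% interval 62% to 77%.

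**The case against.** Several points on the other side have weight.

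- **Survival models.** A reader might infer that Aim 2 yields nothing except mean differences. The protocol does not support that: the secondary hazards models take progression as the outcome. They remain limited. They cover a subset, do not name decompensation (which defines group d), and are tied neither to the Aim 1 panel nor to a discrimination measure.
- **Carry-over from Aim 1.** The opening words of the Aim 2 plan might bring along the secondary multinomial model. The sentence then names only linear regression, so carry-over is unclear; it should be called neither planned nor ruled out.
- **Re-selection.** A reader might infer that AIC and Cp will re-choose proteins on the validation data and turn Aim 2 into a second discovery set. Nothing says so. Section 4.2 has the panel assembled from Aim 1, and with protein as response these criteria cannot choose among proteins.
- **The criteria are not naive.** Cp and AIC penalise complexity with expected prediction error in view. That is true, but the prediction concerned is of protein level, and the claim to ensure reproducibility is still too strong.
- **Too early to specify.** Panel, coefficients and cut-off cannot exist before Aim 1 ends, and Part III requires committee review first. The protocol can still commit to locking them, and it already fixes the primary model.
- **Outcome-based sampling.** Section 4.1 rightly disclaims absolute probabilities. AUC, sensitivity and specificity do not need disease prevalence, though they apply to the sampled mix of patients.

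**Conclusion.** The concern holds for the primary Aim 2 analysis. As written, that analysis estimates group differences in protein level, while the stated purpose is to validate a panel's diagnosis and prediction in patients. The sentence on reproducibility is wrong for this model. The 70% accuracy is not stated to be re-tested in independent patients.

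The gap can be material: at the limiting CV of 0.5, the 27% difference that Aim 2 expects to detect corresponds to about 61% accuracy for a single marker, below the protocol's own gate. That figure rests on normality, equal variances and one protein, and it rises with a smaller CV. The finding itself rests on the wording of sections 4.1 and 4.2, not on this arithmetic. The requested samples are enough for a usable estimate of discrimination, on the assumed AUC of 0.75 and across the range shown.

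**What to change.** 1. State that the panel and its scoring rule (proteins, transformation, coefficients, cut-off) will be locked when Aim 1 ends, before Aim 2 results are analysed.
2. Make the primary Aim 2 analysis the unchanged application of that rule to the baseline sera. Report AUC with 95% confidence intervals for Ishak 5-6 versus 3-4, and for progressors versus non-progressors within each stage (a versus b, c versus d).
3. Report sensitivity, specificity and accuracy at the locked cut-off for the diagnostic contrast. Because that cut-off comes from extreme groups, treat cut-off results for the within-stage contrasts as exploratory.
4. Keep the linear, mixed and survival models as secondary analyses, and say whether the Aim 1 disease-as-response model applies in Aim 2.
5. Delete the claim that adjusted R-squared, Cp and AIC ensure reproducibility. Label any refit exploratory and cross-validate it.

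Cost: changed analysis wording, a scoring rule recorded before Aim 2, and slightly more analysis work. No further patients or samples are needed, since Part III already requests baseline serum from all four groups. The sponsor must accept that the validated accuracy may be lower than in Aim 1.

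### The tentative Aim 2 detectable difference of 27% does not follow from Aim 1's assumptions; with 30 per group it should be about 33%

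*Protocol*

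**What the plan says.** Protocol section 4.1 (Sample Size) sets the Aim 1 basis: "we plan the sample size to detect a relative difference of 40% in protein levels between any two groups of patients". The variability input is given as a bound, "Assuming a coefficient of variation of <0.5", and the result is that "we would have at least 80% power to detect the difference with 20 patients per group". Neither alpha nor sidedness is stated.

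Section 4.2 (Statistical Analysis Plan) carries this forward to the validation study. The sentence opens "Tentatively, using the same assumptions as in Aim 1" and then claims "improved sensitivity with 30 patients per group, instead of 20, resulting in an ability to detect a 27% difference in protein levels".

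The same paragraph concedes that too little is known to assess power for Aim 2, and says that an "updated sample size assessment will be performed after Aim 1 has been completed". The planned group size in section 4.2 and Part III is 30 to 40 in each of four groups; section 4.2 puts it as "We request serum specimens from a total of approximately 150 patients".

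**The concern.** The Aim 2 sentence holds every assumption at its Aim 1 value and credits the gain to the larger group alone. An increase from 20 to 30 per group narrows a standard error by a factor of 0.816, so it cannot bring a 40% detectable difference down to 27%.

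This is the only sensitivity figure given for the validation study, and it errs in the favourable direction. Those asked to release stored serum would take the study to be more sensitive than it is. If the same rule for scaling with n were used in the planned reassessment, the error would recur there even with correct new estimates of variability.

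**Working it through.** **Inputs.** Aim 1 (section 4.1): relative difference 0.40, coefficient of variation (CV) below 0.5 and taken at 0.5, power at least 80%, n = 20 per group. Aim 2 (section 4.2): same assumptions, n = 30 per group, stated result 27%. Alpha and sidedness are not given; 5% is assumed, one-sided and two-sided.

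**Formula.** For two equal groups, with the difference and SD both expressed relative to the mean:

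detectable difference = (z_alpha + z_power) x CV x sqrt(2/n)

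With alpha, sidedness, power and CV fixed, they cancel in the ratio of two detectable differences, which leaves sqrt(n1/n2).

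**Step 1: the basis that reproduces Aim 1.** At CV 0.5 and n = 20 per group, for a 40% difference:
- one-sided 5%: power 81.2% (normal approximation) or 79.9% (t-test); the t-based detectable difference is 40.0%;
- two-sided 5%: power 71.6% (normal) or 69.3% (t-test); 80% is reached only if the CV is at most about 0.45 (normal) or 0.44 (t-test).

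One-sided 5% with CV 0.5 is therefore the basis that matches Aim 1 at its stated bound.

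**Step 2: where 27% may come from.** 40% x 20/30 = 26.7%, which rounds to 27%. This is scaling by 1/n. It is an inference from the number.

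**Step 3: the correct scaling.**
- n = 30: 40% x sqrt(20/30) = 32.7% (t-based, one-sided, CV 0.5: 32.5%)
- n = 40: 40% x sqrt(20/40) = 28.3% (t-based: 28.0%)

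Starting instead from the two-sided basis with the CV lowered until Aim 1 has 80% power, the t-based result at n = 30 is 32.4%. Applying the same scaling to log ratios gives a 34.1% decrease or a 31.6% increase at n = 30.

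**Step 4: what 27% would require.** t-test, CV 0.5:

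| | one-sided 5% | two-sided 5% |
|---|---|---|
| Power for 27%, n = 30 | 66% | 54% |
| Power for 27%, n = 40 | 77% | 66% |
| n per group for 80% power | 44 | 55 |

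The scaling rule alone gives 20 x (40/27)^2 = 43.9, or about 44 per group.

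**Step 5: a consistent two-sided version.** At CV 0.5, two-sided 5%, 80% power, t-test, the detectable differences are 45.5% with 20 per group, 36.8% with 30 and 31.7% with 40. The first of these shows that Aim 1's 40% does not hold on this basis at CV 0.5.

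**The case against.** **The inputs are inequalities.** The CV is given as below 0.5 and the power as at least 80%, so one setting might satisfy both statements. Such settings exist. With a CV of 0.36 (two-sided) or 0.41 (one-sided), power for 27% with 30 per group is about 81%, and power for 40% with 20 per group is 93% or 92%. On a log scale with SD sqrt(ln 1.25) = 0.472 and a one-sided test, a 27% decrease with 30 per group has 82% power and a 40% decrease with 20 per group has 96%. What stands is that 27% is not impossible under every reading. But each of these readings gives Aim 1 92% to 96% power. At those lower CVs, 20 patients per group would already detect about 33%. They do not explain a move from 40% to 27% that the text attributes to 30 patients in place of 20.

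**The figure is tentative and nothing depends on it.** This stands. The protocol says information is insufficient, promises a reassessment using observed variability and group differences, and requires committee review before Aim 2. The 30 to 40 per group is not derived from 27%, and the rule for proceeding is panel accuracy of at least 70%. The tentative label covers uncertain inputs, however, and does not make the calculation from the stated inputs right.

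**The gap narrows at the planned total.** About 150 patients in four groups is 37.5 per group, which gives 40% x sqrt(20/37.5) = 29.2%. This is also fair, but the sentence claims 27% for 30 per group.

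**Stronger readings.** A reader might infer that the validation study is undersized, that its null results will be judged against 27%, or that linear scaling was certainly used. The documents support none of these: no required detectable difference is set for Aim 2, no rule ties interpretation to 27%, and no formula is shown.

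**Conclusion.** The stated 27% does not follow from the protocol's own inputs. With only n changed from 20 to 30 per group, the detectable difference is about 33%, and with 40 per group about 28%. For a comparison of means this ratio does not depend on the unstated alpha or sidedness, or on the power and CV, provided they stay at their Aim 1 values. The power figures do depend on them: 66% with 30 per group and 77% with 40 rest on a one-sided 5% t-test with CV 0.5, which is an assumption chosen because it reproduces Aim 1.

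Severity is moderate to minor. The error lies in a provisional planning statement that is due to be replaced, and correcting it changes no sample, analysis or decision.

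**What to change.** In section 4.2, replace 27% with about 33% with 30 per group (about 28% with 40 per group). State the alpha and sidedness behind both the Aim 1 and Aim 2 figures, and use 1/sqrt(n) scaling in the reassessment after Aim 1.

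If the tests are to be two-sided at 5%, restate both aims on that basis at CV 0.5: about 45% with 20 per group for Aim 1, and about 37% with 30 and 32% with 40 for Aim 2. Quoting the two-sided Aim 2 figures while leaving Aim 1 at 40% would create a new inconsistency.

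On the one-sided basis the cost is one corrected sentence, a statement of alpha and sidedness, and a less favourable figure. The two-sided route also requires the Aim 1 sentence to be rewritten. No extra patients or specimens are needed.

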2.4 The development of MRM peptides for liver-specific proteins. From liver-specific transcripts, we selected 36 proteins as highly specific for liver and known to be detectable in plasma, since they were reported already in the Human Proteome Organization (HUPO) international Plasma Proteome Project led by [name], [name], and [name] and in the PeptideAtlas database (www.peptideatlas.org, [name], ISB). Based on this list of proteins (Table 1), we have designed peptide standards for MRM assays, at least two per protein for most of the proteins. These peptides are unique or highly associated with the particular protein, and are designed to be detectable in the mass spectrometer and quantifiable [Anderson & Hunter, 2006]. These prepared peptides have been extensively tested on Thermo Finnigan LCQ deca instruments with full LC-MS/MS and SRM (selected reaction monitoring) runs. The current list of MRM peptides for liver-specific proteins is included below (Table 1, at end).

Based on the results, MRM transition candidates from each parent peptide standard ion were selected and tested for MRM analysis. We have developed MRM methods to scout several precursor-fragment ion transition pairs from each peptide over a large time period in order to observe elution for each peptide on a Waters nanoAcquity UPLC system coupled to a Waters Quattro Premier XE triple quadrupole mass spectrometer or an Eksigent Tempo nano-LC system coupled to an ABI Q-Trap 4000 mass spectrometer. These observed retention times will be mapped to a time-segmented MRM method capable of analyzing hundreds of peptide precursor-fragment ion transition pairs in a single chromatographic run. Results for peptide standards were obtained that show capturing of transition daughter ions with reasonably strong signals. We create a liver-specific fingerprint by comparing the isotopically-labeled (heavy) peptide standards to endogenous (light) blood protein in mouse or human.

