glycine N-methyltransferase	NP_061833.1	3	AWLLGLLR VWQLYIGDTR SLGVAEGLDQYADGEAAR
argininosuccinate synthetase 1	NP_446464.1	2	BQGYDVIAYLANIGQK GQVYILGR
4-hydroxyphenylpyruvate dioxygenase	NP_002141.1	3	FLHFHSVTFWVGNAAK GYLLQIFTK TEDIITAIR
argininosuccinate lyase	NP_000039.2	3	WSHWILSHAVLTR FVGAVDPIMEK VAEWAQGTF GIVVGIK
aldolase B, fructose-bisphosphate	NM_000035.2	3	ALNDHHVYLEGTLK DGVDFGK
betaine-homocysteine methyltransferase	NP_001704.2	2	VNEAACDIAR AIARELAPER
homogentisate 1,2-dioxygenase	NP_000178.2	2	LLIYTFGK CFYNSDGDPLIVPQK
beta-carotene 15, 15'-monooxygenase 1	NP_059125.2	2	FAVPLHVDK YVFATGVQWSPITPK
glutamate dehydrogenase 1	NP_005262.1	2	YSTDVSDEVK MVEGFFDR
catalase	NP_001743.1	2	HMNGYGSHTFK FYTEDGNWDLVGNNTPIFFIR
retinol-binding protein 4	NP_006735.2	2	YWGVSFLQK FSGTWAMAK
fibrinogen-like 1	NP_004458.3	3	SDGENFNR FSTWDR AQVRLLETR
fructose-1,6-bisphosphatase 1	NP_000498.2	2	TLVYGGIFLYPANK DFDPAVTEYIQK
methionine adenosyltransferase I, alpha	NP_000420.1	3	FVIGGPQDAGVTGR YLEDFTVYHLQPSGR FVIGGPQDAGLTGR
hydroxyacid oxidase 1	NP_060015.1	2	AIFVTVDTPYLGNR LAMALSGCQNVK
aldehyde dehydrogenase 1A1	NP_000680.2	2	IFINNEWHDSVSGK VAFTGSTVEGK
isocitrate dehydrogenase 1	NP_005887.2	2	TVEEAAHGTVTR LIDDMVAQAMK
proteasome alpha 2 subunit	NP_002778.1	2	YNEDLEDAIHTAILTLK HIGLVYSGMSPDYR
DNA directed RNA polymerase II polypeptide B	NP_000929.1	2	MTIHLIECLQK DCQIAGHAAQFLR
glutamate-ammonia Ligase	NP_002056.2	1	DIVEAHYR
asialoglycoprotein receptor 1	NP_001662	1	LLHVK
Asialoglycoprotein receptor 2	NP_550434	2	WVDGTDYR ADHDALLFHLK
Carbamoyl-phosphate synthetase 1, mitochondrial	NP_001866	1	GNDVLVIECNLR LSIQCYLR
3-hydroxy-3-methylglutaryl-Coenzyme A synthase 2	NP_005509	3	YTVGLGQTR VSFEFTEIMNQR SHTGLGR
Transferrin	NP_001054	3	DQYELLCNDTR TAGMNIWGLLYNK TPENFCK
Plasminogen	NP_000292	3	EAQLPVIENK HSIPTETNDR DFHINLFQVLPWLK
complement factor B preproprotein	NP_001701	2	GDSGGPLIVHK IHVYEK
paraoxonase 1	NP_000437	2	HANWTLTPLK IYHSHIDAPK
ceruloplasmin precursor	NP_000087	2	TYCSEPEK SHIAQNSPHTPPR
Interleukin 6 signal transducer	NP_002175	2	HQVPSVQVFSR DFTVLVDR
Peroxisome biogenesis factor 1	NP_000457.1	2	GFLPASLR
Importin 4	NP_078934.3	2	ACYALENFVENLGGPK LLPPLLIQVCK
Purine nucleotide phosphorylase	NP_000261.2	2	FEVGDIMLIR VGFSLITNK ENFSCLTR
Malate dehydrogenase	NP_005908.1	2	LSSAMSAK

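### Section 5c promises 2 or 3 specific peptides for each of the 36 proteins; Table 1 and section 2.4 do not support this, and five listed peptides need a sequence or digestion check before specimens are used

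*Protocol*

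**What the plan says.** Section 5c (Methods & Data Usage, assays of liver and serum specimens) makes a statement about the whole panel: "We will use multiple reaction monitoring of the 2 or 3 specific peptides associated with each of the 36 proteins in the Table below".

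Section 2.4 is more cautious on both parts of that statement. On number, it says "we have designed peptide standards for MRM assays, at least two per protein for most of the proteins". On specificity, it says "These peptides are unique or highly associated with the particular protein, and are designed to be detectable in the mass spectrometer and quantifiable". It also reports prior work on the standards: "These prepared peptides have been extensively tested on Thermo Finnigan LCQ deca instruments".

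Table 1 gives the peptides. The rows that matter here are:
- Glutamate-ammonia ligase: count 1, DIVEAHYR.
- Asialoglycoprotein receptor 1: count 1, LLHVK.
- Methionine adenosyltransferase I, alpha (NP_000420.1): count 3, "FVIGGPQDAGVTGR YLEDFTVYHLQPSGR FVIGGPQDAGLTGR".
- Betaine-homocysteine methyltransferase: count 2, "VNEAACDIAR AIARELAPER".
- Fibrinogen-like 1: count 3, SDGENFNR, FSTWDR and AQVRLLETR.

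The protocol names no digestion enzyme and describes no search of the peptides for uniqueness.

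**The concern.** The study hypothesis concerns organ-specific proteins, and section 2.2 itself treats doubt about a marker's origin as a cause of poor diagnostic specificity. Section 4.1 pairs each protein in liver with the same protein in serum. Both depend on a measured value belonging to the protein whose name it carries.

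A peptide that also occurs in another protein can carry that protein's signal. A peptide with an internal cleavage site can vary with completeness of digestion as well as with protein level. Either kind of value could enter the Aim 1 panel, and so the 70% accuracy rule for starting Aim 2, under the wrong label. Aim 1 draws on flash-frozen liver tissue from up to 40 patients, so the time to settle this is before those specimens are used.

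**Working it through.** **1. Count of proteins and peptides (Table 1).** There are 36 protein rows, so the 36 in section 5c reproduces. The count column has 24 proteins with 2, 9 with 3 and 3 with 1: 24×2 + 9×3 + 3×1 = 78. The printed sequences number 77 if the broken argininosuccinate lyase entry (VAEWAQGTF GIVVGIK) is read as one peptide, which then matches its count of 3; they number 78 if it is split.

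**2. Does each protein have 2 or 3?** By the count column, 33 of 36 do. The three with a count of 1 are glutamate-ammonia ligase, asialoglycoprotein receptor 1 and carbamoyl-phosphate synthetase 1. The last prints two sequences, "GNDVLVIECNLR LSIQCYLR", so it is set aside. Other rows where count and sequences disagree may also reflect text extraction and are not counted. Two proteins fall short on both count and sequence: 2/36 = 5.6%. Section 5c is therefore inexact for at least two proteins, whatever happened in extraction.

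**3. LLHVK.** It has 5 residues and is the shortest entry; three others have 6 (MFMAYK, FSTWDR, IHVYEK). It is the only peptide for its protein, so no second peptide could expose interference. Leucine and isoleucine have equal mass, so LLHVK, LIHVK, ILHVK and IIHVK share a precursor mass. As an illustration only:

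expected other matches = N × P(K or R before) × P(L or I)² × P(H) × P(V) × P(K)

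Assuming average residue frequencies and a proteome of N = 5 to 11 million residues (neither is in the protocol), this gives 1.03 to 2.26. The chance of no other match is exp(−1.03) = 0.36 to exp(−2.26) = 0.10. If only the exact sequence LLHVK counts, about 0.5 to 1.1 matches are expected and the chance is about 0.60 to 0.33. The same approach gives about 0.0001 matches for the eight-residue DIVEAHYR, so glutamate-ammonia ligase is a count issue only.

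**4. Methionine adenosyltransferase.** FVIGGPQDAGVTGR and FVIGGPQDAGLTGR each have 14 residues and differ only at residue 11 (V or L). They are the only pair of equal-length peptides in Table 1 that differ at two residues or fewer. One site in one sequence cannot yield both. Barring a repeated segment or a sequence variant, one of the two does not belong to NP_000420.1. They differ in mass, so the instrument can tell them apart; the question is which belongs to the named protein.

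**5. Internal arginine.** With the broken entry joined, all 77 sequences end in K or R, which suggests trypsin. Only AIARELAPER and AQVRLLETR contain a K or R before the end that is not followed by P. If trypsin is used, both are missed-cleavage forms that complete digestion would remove.

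**6. Reach.** Proteins carrying a flagged peptide: 4/36 = 11.1%. Of these, three have other listed peptides: VNEAACDIAR for betaine-homocysteine methyltransferase; SDGENFNR and FSTWDR for fibrinogen-like 1; YLEDFTVYHLQPSGR plus whichever V/L variant matches for methionine adenosyltransferase. Proteins resting wholly on a flagged peptide: 1/36 = 2.8%.

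**The case against.** A reader might infer that these peptides cannot measure the named proteins, or that 4 of 36 panel values would be wrong. The documents do not support either. Uniqueness, and the match to NP_000420.1, need a sequence database. Trypsin is inferred from the peptide ends. The chance-match figures rest on assumed frequencies and count every protein, whether or not it is detectable in serum. Three of the four proteins can be measured from other listed peptides, and the protocol states no rule for combining peptides; such a rule could properly sit in an analysis plan that is not shown. Uneven digestion biases a group comparison only if it differs between groups; otherwise it adds noise. All of this stands.

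It can also be said that section 2.4 already discloses the exceptions and reports extensive testing. The disclosure is real, but it is what makes section 5c inconsistent with the rest of the protocol. The testing described is of synthetic standards. A standard can perform well whether or not its sequence is unique in serum. Fragment transitions, retention times and labelled spikes help against different sequences of similar mass, but they would not separate an identical sequence from another protein. A spiked peptide also does not correct for incomplete cleavage of the patient's own protein. Independent specimens in Aim 2 limit reliance on any one marker but do not check its identity.

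**Conclusion.** The concern holds in a limited form. Section 5c is contradicted by Table 1 for at least two of 36 proteins and claims more than section 2.4 does. Five peptides in four proteins (LLHVK, the V/L pair and the two with an internal arginine) may not specifically quantify the protein they are listed under, and no documented check settles it. Only asialoglycoprotein receptor 1 depends entirely on such a peptide.

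The count conflict needs no assumption. The internal-arginine point assumes trypsin. The V/L point assumes no repeated segment or sequence variant. The LLHVK point says only that uniqueness cannot be presumed. No effect on the 70% decision rule has been shown or quantified. The correction is worth making because marker identity underlies the hypothesis and the check is cheap.

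**What to change.** Before any specimen is used:
- Check every Table 1 peptide against its listed accession and for uniqueness, treating leucine and isoleucine as the same. This would also settle BQGYDVIAYLANIGQK, whose first letter is not a single standard residue code and may be a typing or extraction fault.
- Quantify methionine adenosyltransferase only from peptides that match NP_000420.1.
- Quantify betaine-homocysteine methyltransferase and fibrinogen-like 1 from their other listed peptides, unless complete and reproducible release of the internal-arginine peptides is shown.
- Replace LLHVK, or leave asialoglycoprotein receptor 1 out of the panel if LLHVK is not unique.
- Correct section 5c to one to three peptides per protein.
- Where a protein has two or more valid peptides, check that they agree. Flag single-peptide proteins as such and do not exclude them; a general requirement for agreement between peptides could never be met by those proteins.

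The cost is a sequence check, possibly one replacement peptide, and a wording change. No patients or extra serum are needed. The downside is that one protein may be lost and two or three others would rest on fewer peptides; betaine-homocysteine methyltransferase would go from two to one.
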